To date, the 20 clinical trials that have been completed or are currently ongoing have enrolled over 600 subjects in the electroporation arms of the studies (including subjects receiving either the DNA vaccine candidate or placebo). The device has been used for administration of DNA injections of up to 1.0 ml volume and 4.0 mg DNA dose per injection site. Subjects have received the vaccine candidate either as a single injection in one muscle site (total DNA dose up to 4.0 mg per administration time point) or as 2 injections in 2 separate muscle sites (total DNA dose up to 8.0 mg per administration time point). Subjects given the DNA dose as a single injection have received up to 5 TDS-IM injections and up to 4.0 mg DNA, and subjects administered with the DNA dose in 2 injections received up to 10 administrations (i.e., 20 total TDS-IM injections).

Acute adverse responses associated with the use of the device include transient pain associated with electroporation-induced localised muscle contractions reported by virtually all subjects. This has occasionally been accompanied by mild paresthesia in the administered limb lasting for several seconds to minutes after application of electroporation. Mild, transient bleeding at the sites of electrode/needle penetration is commonly observed following removal of the device from the administration site. Local site reactogenicity, including injection site soreness, erythema, and/or induration of mild to moderate severity, has been commonly reported following electroporation-mediated DNA delivery. Mild to moderate bruising at the administration site has been observed occasionally. The local site reactions typically resolve within 24-72 hours following administration, but, in rare instances, local site soreness has been reported to persist for up to one week.

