6.1.3 Immunisation schedule

The doses, methods and schedule of immunisation are described in **Table 1** below.

Table 1: Schedule of Doses and Methods of Immunisation

Group	Method of immunization; Dose of DNA			Method of immunization; Dose of CN54gp140
	Dose 1 at WK 0	Dose 2 at WK 4	Dose 3 at WK 8	Dose 4 at WK 20
1 N=8	0.6mg ID*/ EP 2mg IM**	0.6mg ID*/ EP 2mg IM**	0.6mg ID*/ EP 2mg IM**	50ug ID***
2 N=8	0.6mg ID* 2mg IM**/ EP	0.6mg ID* 2mg IM**/ EP	0.6mg ID* 2mg IM**/ EP	50ug ID***
3 N=8	0.6mg ID*/ EP 2mg IM**/ EP	0.6mg ID*/ EP 2mg IM**/ EP	0.6mg ID*/ EP 2mg IM**/ EP	50ug ID***

* 1 x 0.15ml injections ID via a needle - into the upper arm with or without electroporation (EP).

** 1 x 0.5ml injections IM – into the upper thigh with or without electroporation (EP).

*** 1 x 0.1ml injections ID via a needle - into the upper arm.

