7.2 Screening Assessments

7.2.1 Demographics, Medical History and Examination

Demographic information such as age, and ethnic origin will be collected at screening and entered onto the screening CRF.

A past and current medical history will be collected at screening during a face to face structured interview using a case report form, including details of any previous reaction to vaccination, allergies, history of epileptic fit, reproductive and respiratory symptoms, contraceptive practices (current method and the length of time using the method), and smoking, alcohol, steroid use and illicit drug history.

The general examination will include weight (kg), height (cm), calculation of BMI, temperature, arm and thigh circumference, blood pressure, inspection of the skin to exclude severe eczema and respiratory, cardio-vascular, abdominal, and neurological examination. Skin fold thickness will be assessed within the upper right and left thigh. An assessment of cervical, axillary and inguinal lymph nodes will also be undertaken.

An ECG will be done to exclude cardiac arrhythmia or palpitations [e.g., supraventricular tachycardia, atrial fibrillation, frequent ectopy, or sinus bradycardia (i.e., <50 beats per minute on exam)]

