7.4.3.2 Urine

- protein, ketones, blood, leukocyte esterase, and nitrites – by dipstick

A urine specimen will be sent to the laboratory if the level of protein, blood, leukocyte esterase or nitrites is considered clinically relevant.

Various local and systemic adverse events are known to be associated with licensed vaccines, and are referred to as '**solicited adverse events**'. These include disturbances in routine laboratory parameters, and are described in **table 2** below.

Information on solicited adverse events will be collected on the day of each immunisation (pre-immunisation, and at 10 and 60 minutes post-immunisation), at a safety call the day after each immunisation and for the following 7 days through a structured interview and examination according to the schedule.

In addition systemic laboratory adverse events will be collected through routine laboratory testing according to the schedule. These will be recorded on the appropriate CRF page.

Participants will also be asked to complete a diary card recording solicited adverse events that start within 7 days of each immunisation.

Table 2: Solicited Adverse Events

Type	Event
Local AEs (immunisation site)	Discomfort Redness Swelling (soft) Induration (hard) Blisters
Systemic Clinical AEs	Abnormally raised temperature Chills Myalgia/flu-like general muscle aches Malaise (excess fatigue) Headache Nausea Vomiting
Systemic Laboratory AEs	Abnormalities in: Creatinine, AST, ALT, alkaline phosphatase, total bilirubin, glucose Hb, total WCC, neutrophils, lymphocytes, platelets

The events will be **graded** according to the study specific toxicity table (see **Appendix 2**).

Relationship to study product, which is defined in **section 8**, will be recorded in the immunisation CRF but not on the diary card, on the assumption that any of these events starting within 7 days of an immunisation are at least possibly related. If the onset is beyond 7 days, the event will be recorded on the adverse event CRF and a relationship determined by the investigator reviewing the event.

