10.2 Endpoints

10.2.1 Primary Endpoints

10.2.1.1 Safety

- Grade 3 or above local solicited adverse event (**Table 2**)
- Grade 3 or above systemic clinical and laboratory solicited adverse event (**Table 2**)
- Any grade of adverse event that results in a clinical decision to discontinue further immunisations
- Any grade of adverse event within 7 days of receiving intradermal and standard intramuscular vaccinations with or without electroporation

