Erythema at injection site	Erythema up to and including 50% of baseline arm circumference OR Symptoms of irritation that are easily tolerated and do not require repeated medication OR Both	Erythema greater than 50% of the arm circumference at baseline With or without Symptoms of irritation that do not require repeated medication OR Symptoms of irritation that require repeated medication AND erythema up to and including 50%	Erythema greater than 50% of the arm circumference at baseline AND symptoms of irritation requiring repeated medication	Hospitalisation
Blistering or ulceration at injection site	Fluid filled vesicles or superficial disruption of epithelium covering an area < 1cm	Fluid filled vesicles or superficial disruption of epithelium, area 1 - 2cm OR Blood filled vesicles OR Full thickness disruption of epithelium healed within 2 weeks	Full thickness disruption of epithelium not healed within 2 weeks	Necrosis
Soft swelling – local	Swelling <25% of arm	Swelling 25-50% of arm	Swelling >50% of arm Or Induration/hardened swelling (when considered by the	

			clinician to be associated with a process arising in the muscle)	
--	--	--	--	--

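### Appendix 2 gives no thigh reference for redness and swelling, and no grade below 3 for muscle-origin hardening, so grade 3+ local events at the IM site may be misgraded

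*Protocol*

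**What the plan says.** **Injection sites.** In Protocol section 6.1.3 (Table 1), the ID DNA dose goes "into the upper arm with or without electroporation (EP") and the IM dose "into the upper thigh with or without electroporation (EP"). This holds for all three groups at weeks 0, 4 and 8.

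**Endpoint and scale.** Protocol section 10.2.1.1 and SAP section 3.1.1 make "Grade 3 or above local solicited adverse event" a primary safety endpoint. Solicited events are graded "according to the study specific toxicity table", which is Appendix 2.

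**Redness and swelling in Appendix 2.** The extent criterion for redness is half of the baseline arm circumference, with "Erythema greater than 50% of the arm circumference at baseline" at the start of both the grade 2 and grade 3 cells. Soft swelling is graded as under 25%, 25–50% or over 50% of the arm. Neither row has a thigh version. Section 7.2.1 nevertheless has "arm and thigh circumference" recorded at screening.

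**Induration.** Table 2 of both documents lists induration separately from soft swelling, and SAP Table 5a has a grade 1–4 shell for it. In Appendix 2 as supplied, it appears only in the grade 3 soft-swelling cell, as "Induration/hardened swelling (when considered by the" clinician to originate in the muscle. For the IM device, section 2.2.2.3 says that soreness, redness and/or "induration of mild to moderate severity, has been commonly reported following electroporation-mediated DNA delivery".

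**The concern.** A grade that depends on the extent of a reaction needs a stated reference at each site where reactions are collected. Here the reference fits the ID site and not the IM site. Separately, a reaction that the protocol's device history calls mild to moderate has, when it arises in muscle, only one grade available, and that grade is 3.

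Grade 3 is the threshold for the local primary safety endpoint and for the display in SAP Table 2. It also enters section 2.2.4, where the proportion of participants with a grade 3+ solicited event helps to define unacceptable safety and so whether a route is pursued. Section 8.1 treats every solicited event starting within 7 days as an adverse reaction, so a causality judgement would not filter out a misgraded event.

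**Working it through.** **1. Match each site to its reference.**

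| Site | Doses | Reference in Appendix 2 | Fits? |
|---|---|---|---|
| Upper arm (ID) | DNA at weeks 0, 4, 8; protein at week 20 | Arm | Yes |
| Upper thigh (IM) | DNA at weeks 0, 4, 8 | Arm | No thigh reference stated |

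The protocol separates the limbs elsewhere: exclusion criterion 8 describes a past severe local reaction separately for thigh and arm. Discomfort and blister grades do not use limb size and are unaffected.

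**2. What the limb reference changes.** The documents give no circumferences. I assume arm 25–35 cm and thigh 45–65 cm.

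- Half the arm: 0.5 × 25 = 12.5 cm to 0.5 × 35 = 17.5 cm.
- Half the thigh: 0.5 × 45 = 22.5 cm to 0.5 × 65 = 32.5 cm.
- Half the arm as a share of the thigh: 12.5/65 = 19% to 17.5/45 = 39%; at 30 and 55 cm, 15/55 = 27%.

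At 30 and 55 cm, a thigh reaction between 15 and 27.5 cm is over the cut-off on the arm reading and under it on a thigh reading. For redness, this decides grade 2 or 3 only if irritation also needs repeated medication; otherwise it decides grade 1 or 2. Soft swelling over 50% is grade 3 with no further condition, but that row says percent of arm without naming circumference, so the arithmetic carries over only by assumption.

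**3. Set the induration texts side by side.**

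- Section 2.2.2.3: mild to moderate after IM electroporation.
- Table 2 and SAP Table 5a: a separate solicited event, grades 1–4.
- Appendix 2: muscle-origin hardening of any size is grade 3; no grade 1 or 2 is given.

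These cannot all be followed. The Appendix 2 wording names muscle, not a limb, so it applies at the thigh as written. Its fault is the missing lower grades.

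**4. Effect on the reported proportion.** SAP Table 3 reproduces at n = 8 with z² = 3.84:

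- 0/8: Wilson upper limit = z²/(n + z²) = 3.84/11.84 = 32%. The SAP prints 0–32%.
- 1/8: centre (0.125 + 3.84/16)/(1 + 3.84/8) = 0.247, half-width 0.224, giving 2–47%. The SAP prints 2–47%.

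One regraded participant therefore moves a group from 0% (0–32%) to 12.5% (2–47%).

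**5. Effect on a test of grade 3+ events alone.** Two-sided Fisher at 8 v 8 with none in one group is p = 2 × C(8,k)/C(16,k):

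- 0 v 3: 2 × 56/560 = 0.20
- 0 v 4: 2 × 70/1820 = 0.077
- 0 v 5: 2 × 56/4368 = 0.026

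About five regraded participants in one group would be needed for a nominal difference.

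**6. Which groups.** All three groups have a thigh IM dose, so the arm reference applies to each. Only groups 2 and 3 (8 + 8 = 16 participants) have IM electroporation, so the hardening rule could fall more on them.

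**The case against.** **Investigators may grade sensibly.** Section 10.4.4 has clinical investigators grade all safety endpoints, and they have a thigh measurement. A reader might infer that IM-site events *are* misclassified. The documents do not show that; they show that the thigh grade is undefined and that grading could be inconsistent.

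**A fallback scale exists.** Appendix 2 and section 7.4.1 refer events outside the tables to FDA guidance. Hardening not attributed to muscle could be graded that way. Redness, swelling and muscle-origin hardening are in the table, so the fallback does not clearly cover them.

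**Layout.** The soft-swelling row is the last in the supplied table and is visibly broken. The formatted original should be checked for a further induration row.

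**Size.** A reader might assume that 10–20% of IM/EP doses cause muscle hardening and infer that 1 − 0.9³ = 27% to 1 − 0.8³ = 49% of participants would have a grade 3 event over three doses. The documents do not support this. They call soreness, redness and/or induration common as a bundle, give no rate for muscle-origin hardening, and do not say that doses act independently.

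**Hold and discontinuation.** A reader might infer that the hold rule would be triggered. Sections 6.1.5 and 7.5 also require non-resolution within 72 hours, and section 2.2.2.3 says that local reactions typically resolve within 24–72 hours. Exposure there is limited, though not nil.

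**Group comparison.** SAP section 4.5.1 compares participants with any endpoint in section 3.1.1, which includes adverse events of any grade within 7 days of vaccination. On that pooled reading, a participant with hardening in the window counts at grade 1 or grade 3 alike. This objection stands: regrading changes the grade 3+ display, not the pooled test. The secondary endpoint is also any-grade.

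**Conclusion.** The point holds as a definitional inconsistency that reaches a primary endpoint. Redness and swelling at the IM site have no valid stated limb reference, and muscle-origin hardening has no grade below 3, contrary to section 2.2.2.3 and SAP Table 5a. Grade 3+ events of these three types may be misgraded.

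The exposure lies in the descriptive grade 3+ results and the section 2.2.4 criterion, where one participant is 12.5 percentage points of a group. An effect on the tests or the hold rule is less likely. The hardening rule is the part that could distort the comparison between groups. Its direction would be towards more grade 3 events in groups 2 and 3, but its size cannot be estimated from the documents. The arm-to-thigh shares (19–39%) rest on assumed circumferences.

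**What to change.** Reconcile Appendix 2 with the injection sites in Table 1, the limb measurements in section 7.2.1, the device experience in section 2.2.2.3 and SAP Table 5a. State once, and consistently, which limb reference applies at each site and how induration maps to grades. Because these grades also feed discontinuation and hold rules, the choice of reference and grades belongs to the sponsor; none is proposed here.

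Before the grade 3+ endpoint is derived, re-check IM-site redness, swelling and induration already graded, and footnote any that cannot be resolved.

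The cost is wording in the toxicity table and SAP plus a small review. Thigh circumference is already collected. The documents do not show that lesion extent was recorded in a form that permits regrading, so the re-check goes only as far as the data allow.

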CUTHIVAC 002

Statistical Analysis Plan

Version: **v1.0**

Date: **10/10/2017**

Authors:

Name: **[name]**

Signature:

Approvals:

Name:

Signature:

Revision History:

Version	Author	Date	Reason for Revision

Contents

1.	Trial overview.....	3
1.1.	Primary Objectives.....	3
1.2.	Secondary Objectives.....	4
1.3.	Exploratory Objectives.....	4
2.	General Considerations.....	4
2.1.	Randomisation	4
2.2.	Sample Size	4
2.3.	Analysis datasets.....	4
2.4.	Missing Data.....	4
3.	Endpoint Definitions	5
3.1.	Primary Endpoints.....	5
3.1.1.	Safety	5
3.1.2.	Immunogenicity	5
3.2.	Secondary Endpoint.....	6
3.2.1.	Safety	6
3.3.	Exploratory Endpoints.....	6
3.3.1.	Immunogenicity	6
3.3.2.	Tolerability	6
4.	Statistical Analyses.....	6
4.1.	Enrolment Description	7
4.2.	Baseline Characteristics	7
4.3.	Follow-up Description.....	8
4.4.	Interim Analysis.....	8
4.5.	Primary Analysis.....	8
4.5.1.	Safety	8
4.5.2.	Immunogenicity	8
4.6.	Secondary Analysis.....	8
4.6.1.	Safety	8
4.7.	Exploratory Analysis.....	9
4.8.	Subgroup Analysis.....	9
A.	Tables	10

1. Trial overview

CUTHIVAC002 is an open-label randomised phase I study aimed at exploring the safety and immunogenicity of two different modes of delivery of a deoxyribonucleic acid (DNA) vaccine (DNA-C CN54ENV) via combined intramuscular (IM) and intradermal (ID) methods with and without electroporation (EP), and boosted with recombinant HIV CN54gp140 administered by intradermal injection in healthy volunteers. The aim of this study is to identify optimal DNA delivery conditions for promoting enhanced antibody responses to boosting with recombinant protein by the intradermal method.

Participants are randomised 1:1:1 to ID/EP, IM/EP or ID/IM/EP, the randomisation is unblinded. Following the immunisation schedule of table 1, participants return at weeks 4, 8 and 20. Primary immunogenicity assessment is at week 22.

Table 1: Immunisation schedules

Group	Immunization: Dose of DNA			Immunization: Dose of CN54gp140
	Dose 1 at WK 0	Dose 2 at WK 4	Dose 3 at WK 8	Dose 4 at WK 20
1 N=8	0.6mg ID*/ EP 2mg IM**	0.6mg ID*/ EP 2mg IM**	0.6mg ID*/ EP 2mg IM**	50ug ID***
2 N=8	0.6mg ID* 2mg IM**/ EP	0.6mg ID* 2mg IM**/ EP	0.6mg ID* 2mg IM**/ EP	50ug ID***
3 N=8	0.6mg ID*/ EP 2mg IM**/ EP	0.6mg ID*/ EP 2mg IM**/ EP	0.6mg ID*/ EP 2mg IM**/ EP	50ug ID***

* 1 x 0.15ml injections ID via needle – into upper arm with/without electroporation (EP)

** 1 x 0.5ml injections IM – into the upper thigh with/without electroporation (EP)

*** 1 x 0.1ml injections ID via a needle - into the upper arm

1.1. Primary Objectives

To evaluate the safety and immunogenicity of an HIV-1 DNA vaccine delivered via combined intramuscular and intradermal methods with and without electroporation, and boosted with CN54gp140 administered by intradermal injection with the aim of identifying optimal conditions capable of promoting enhanced antibody responses to HIV.

1.2. Secondary Objectives

To compare the safety of the electroporation devices to standard intramuscular or intradermal injections.

1.3. Exploratory Objectives

To describe qualitative differences between the different methods of delivery in terms of changes from baseline in overall magnitude and functionality of antibody responses to the vaccines, and quantitative differences in cellular responses (CD4+ and CD8+ T cells).

To evaluate the tolerability of vaccination using the electroporation devices.

2. General Considerations

2.1. Randomisation

Participants will be block-randomised using a computer-generated algorithm with a back-up manual procedure and randomisation will be stratified on the basis of gender. The randomisation lists are generated and checked by the trial statistician, and stored securely in the trial database.

Participants are randomised 1:1:1 to ID/EP, IM/EP or ID/IM/EP. Randomisation is unblinded.

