1.1.2 Disease/participants studied

Healthy male and female volunteers 18 to 50 years old who are at low risk of HIV infection are to be recruited. For more details refer to **Section 4**.

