10. STATISTICAL CONSIDERATIONS

10.1 Method of Randomisation

Participants will be block-randomised centrally using a computer-generated algorithm with a back-up manual procedure. Randomisation will be stratified on the basis of gender.

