2.2. Sample Size

It is not the remit of this Phase I trial to recruit a sufficient number of participants to be statistically confident about the differences between groups. By the end of this study 8 participants will have been randomised to each method of delivery.

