4.5. Primary Analysis

4.5.1. Safety

For each arm the proportion and its 95% CI will be reported for participants with a primary safety endpoint as defined in 3.1.1. The proportion with events will be compared in a pairwise manner between the three randomised groups, using Fisher's exact tests.

Grade 3 or above safety endpoints and any endpoints that lead to discontinuation of the vaccine regimen will be described, and a full listing of all events for each participant will be filed in the statistical master file.

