4.5.2. Immunogenicity

Endpoint titres (concentration) of systemic CN54rgp140-specific IgG antibodies at 4 weeks from the final vaccinations will be described (mean and 95% C.I. – log10 scale - or median and IQR – original scale) by group for the responders, and compared using the Wilcoxon rank-sum test.

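### The primary antibody comparison ignores gender, the one factor used to stratify randomisation, and would lose power if titres differ clearly by gender

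*SAP*

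**What the plan says.** Both documents stratify the allocation by gender and by nothing else. Protocol 10.1 states: "Randomisation will be stratified on the basis of gender". SAP 2.1 repeats that "randomisation will be stratified on the basis of gender" and adds "Participants are randomised 1:1:1 to ID/EP, IM/EP or ID/IM/EP". Block size is not given. SAP 2.2 sets the numbers: "By the end of this study 8 participants will have been randomised to each method of delivery". Protocol 1.1.2 admits "Healthy male and female volunteers 18 to 50 years old" and neither document fixes the mix of men and women.

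Gender appears in none of the SAP sections that specify between-arm tests:
- SAP 4.5.2 (primary antibody endpoint): titres are described "by group for the responders, and compared using the Wilcoxon rank-sum test".
- SAP 4.5.1 (primary safety): proportions are "compared in a pairwise manner between the three randomised groups", by Fisher's exact test. SAP 4.6.1 does the same for secondary safety.
- SAP 4.7 (exploratory): Fisher's exact test for categorical outcomes and Welch tests for continuous ones.

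No reason is given for leaving the stratification factor out. Neither document states an alpha level, an effect size or a power for any of these tests. Protocol 2.2.1 says the trial is not sized for formal comparison of the groups and that the immunology is mainly for description. Protocol 10.3 declines to estimate power for titres because it depends on how many participants respond.

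**The concern.** Stratified allocation evens out gender across the arms, so gender contributes little to the observed arm difference. A test that ignores gender still counts the spread between men and women as random error. It therefore overstates the uncertainty of the arm difference: it rejects less often than its nominal level when the arms are the same, and detects less when they are not.

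The antibody comparison is where this could matter. It is the primary immunogenicity analysis, it has at most 8 participants per arm, and a p-value is planned despite the descriptive purpose. Protocol 2.2.4 also sets out an expectation that group 3 will show significantly greater antibody responses than the other groups, with a view to shaping later trials. If a p-value is to be reported, it is better that it match the randomisation.

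**Working it through.** **Inputs.** From the documents: 8 per arm, 1:1:1, gender the only stratum, Wilcoxon rank-sum on responders. Assumed, because the documents give no figure: two-sided 0.05; normal log titres with SD 1 within gender; a gender difference *g* of 0 to 1.5 SD (2 SD in some runs); 4 men and 4 women per arm unless stated; an arm shift of 1.33 or 1.5 SD.

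**The plan's own figures.** There is no power figure to reproduce. The only precision figures for a group of 8 in the SAP are the Wilson intervals in its Table 3, and these reproduce. For 0/8 the upper limit is z²/(n + z²) = 3.84/(8 + 3.84) = 32%, as printed.

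**Step 1: mechanism.** With 4 men and 4 women in each arm, the true variance of the difference in arm means is 1/8 + 1/8 = 0.25, whatever *g* is. A test that ignores gender estimates the within-arm variance from a sum of squares with expectation 6 (within gender) plus (4×4/8)(g² + 1/4 + 1/4) = 2g² + 1 (between genders). Divided by 7 degrees of freedom this is 1 + 2g²/7. The standard error is too large by about √(1 + 2g²/7):
- *g* = 0.5: √1.071 = 1.04
- *g* = 1: √1.286 = 1.13
- *g* = 1.5: √1.643 = 1.28

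This is the mean-based version. The rank test behaves in the same way. It also shows why a gender effect of 0.5 SD hardly matters.

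**Step 2: power of the antibody test.** Simulation with all participants responding, arm shift 1.33 SD, exact Wilcoxon against aligned ranks with all 70 × 70 = 4,900 within-gender permutations:

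| Gender effect (SD) | Planned Wilcoxon | Gender-stratified aligned ranks |
|---|---|---|
| 0 | 68% | 65% |
| 0.5 | 66% | 66% |
| 1 | 58% | 65% |
| 1.5 | 46% | 66% |

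Repeat simulations agree within about 2 points. At 3,000 trials per setting the Monte Carlo standard error at 60% power is √(0.6×0.4/3000) = 0.9 points. Type I error of the planned test at 1.5 SD is about 1% (1.2% and 1.4% in two runs). The stratified test stayed between 3.9% and 5.4%. With a 6/2 gender mix, power at 1.5 SD is 51% v 65%, so the result does not depend on an even split.

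**Step 3: a larger shift and a model.** At an arm shift of 1.5 SD and *g* = 0 / 1 / 2 SD, the planned Wilcoxon has type I error 0.049 / 0.027 / 0.006 and power 78% / 68% / 41%. A linear model with a gender term has type I error 0.050 / 0.050 / 0.052 and power 79% throughout.

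**Step 4: responders only.** SAP 4.5.2 drops non-responders. With 80% responding in each gender and a 1.5 SD shift, the planned test has type I error 0.041 / 0.026 / 0.008 and power 60% / 50% / 26% at *g* = 0 / 1 / 2 SD. At a 1.33 SD shift, planned v stratified power is:
- 70% responding: 40% v 41% at *g* = 0.5 and 32% v 39% at *g* = 1
- 50% responding: 16% v 16% and 15% v 17%

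Selecting responders can also undo the gender balance. Given a strong imbalance (4 men and 1 woman against 1 man and 4 women), type I error of the planned test is 0.064 at *g* = 1 and 0.115 at *g* = 3. The test is therefore conservative on average, not in every realised sample.

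**Step 5: the safety tests.** Exact enumeration, 8 v 8, Fisher against an exact gender-stratified conditional test; event rates (men/women) are assumed:

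| Mix per arm | Rates, one arm v other | Fisher | Stratified exact |
|---|---|---|---|
| 4/4 | 5%/35% v 65%/95% | 59.7% | 60.1% |
| 4/4 | 10%/30% v 60%/85% | 44.5% | 44.8% |
| 6/2 | 5%/35% v 65%/95% | 59.7% | 55.7% |
| 6/2 | 10%/30% v 60%/85% | 41.9% | 36.1% |

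Stratifying gains 0.3 to 0.4 points at 4/4 and loses 4.0 to 5.8 points at 6/2. With 30% events in everyone, and so no gender effect at all, Fisher's type I error is already only 1.2%, and the stratified test at 4/4 has the same 1.2%. A gender difference can lower Fisher's error further (0.5% at rates of 10% and 50%), but most of the shortfall from 5% is discreteness at n = 8.

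**The case against.** The best defence is that nothing the plan promises is broken. It claims no power, names no alpha, and treats the immunology as description. The Wilcoxon test is simple, and under stratified allocation its average error is towards caution. No document reports that antibody responses to these products differ by gender. At 0.5 SD or less, adjustment brings no worthwhile gain, and with few responders neither test has useful power. The usual remedy can also do harm: the exact van Elteren test is so discrete at 4 v 4 per stratum that it gave 54% power against 67% for the plain test when gender had no effect.

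Most of this stands, and it limits the weight of the point. It does not remove it. SAP 4.5.2 still specifies a significance test for a primary endpoint, and a description of purpose does not make that test match the design. The van Elteren difficulty is a reason to choose a different stratified method: aligned ranks or a linear model cost far less.

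**Conclusion.** The point holds for the antibody comparison, conditionally and at low priority. If log titres differ by about 1 SD or more between men and women, the planned Wilcoxon test gives up about 7 points of power at 1 SD (58% v 65%) and about 20 at 1.5 SD (46% v 66%). At 0.5 SD there is no difference, and at zero the planned test is slightly better. These figures rest on normal log titres, a 4/4 mix, a 1.33 SD shift and everyone responding. With fewer responders both the absolute power and the gain shrink.

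A reader might infer two stronger things. One is that every between-arm test should be stratified, including safety. The enumeration does not support that: at 8 per arm a stratified exact test gains almost nothing and can lose several points. The other is that the planned test's error rate simply is below nominal. That follows only if a gender effect exists, which the documents do not establish, and only on average, since a responder subset with unbalanced gender can push the error above 5%. The planned test is not invalid. It leaves out a factor that the design has already paid for.

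**What to change.** In SAP 4.5.2:
- Pre-specify a gender-stratified comparison of titres. Either aligned ranks permuted within gender, or a linear model on log10 titre with arm and gender, would serve. Name one.
- Keep the unstratified Wilcoxon test as a check.
- State a fallback to the unstratified test if a gender stratum has no responders in an arm, and report responder counts by arm and gender so that any imbalance is visible.

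Leave the Fisher tests in SAP 4.5.1 and 4.6.1 unchanged. If the team prefers not to change the primary test, the least that is needed is a sentence saying that the comparison is descriptive, ignores the stratification factor, and is likely to be conservative if titres differ by gender.

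The cost is SAP wording and a few lines of code, plus about 2 to 3 points of power for aligned ranks if gender turns out not to matter. In the simulations at a 1.5 SD shift, the linear model lost nothing against the Welch test in that case (79% for both), but it relies on roughly normal log titres.
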